6.3 Analysis of Secondary Outcomes

The key secondary outcome of effectiveness of mPATH-CRC will be evaluated by comparing the proportion who complete CRC screening within 16 weeks of their index visit to the clinic between a pre-implementation cohort (months 12 - 4 before implementation) and a post-implementation cohort (months 1 - 8 after implementation). Similar to the model described for mPATH-CRC Reach above, effectiveness of mPATH-CRC will be evaluated using a mixed effects logistic regression model. For an overall assessment of the effectiveness, completing CRC screening within 16 weeks (Y/N) will be the patient-level outcome, implementation cohort will be the primary independent variable, site will be a random effect, and the stratification factor clinic size will be a covariate per the design. Pre- vs post-implementation changes will also be compared between the “high touch” and “low touch” implementation strategies and between dose levels defined based on mPATH™-CRC usage by incorporating interactions into the mixed effects logistic regression models. An interrupted time series analysis (segmented

EFFECTIVENESS AND IMPLEMENTATION OF MPATH-CRC: A MOBILE HEALTH SYSTEM FOR

COLORECTAL CANCER SCREENING

Wake Forest Baptist Comprehensive Cancer Center (WFBCCC)

WFBCCC # TBD

regression)^{77,78} will also be used to estimate the effect of the intervention within each clinic (using interaction terms with clinic within a linear model) adjusting for any trend that was occurring in screening prior to the implementation. This model provides estimates of the time trends before and after the intervention as well as the change in screening rates due to the intervention. Linear contrasts will be used to compare the changes in screening rates and trends between the “high touch” clinics and the “low touch” clinics. As in Section 6.2, we will assess the effects of cluster- and patient-level covariates and their interactions with implementation strategy in secondary analyses. The same basic approach outlined in Section 6.2 will also be used to compare other binary implementation outcomes between the “high touch” and “low touch” strategies. Continuous implementation outcomes are measured at the provider/staff level, rather than the patient level. Linear mixed effects models will be used to compare these outcomes between the “high touch” and “low touch” strategies, with implementation approach as the primary independent variable, site as a random effect, and the stratification factor clinic size as a covariate per the design.

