mPATH-CRC is our iPad-based application, designed for individuals with low literacy, which patients use during routine health care visits.³⁶ Because most Americans over age 50 have seen a doctor within the past year, including 75% of adults with less than a high school education, interventions in medical practices have a potential broad reach.³⁷ mPATH-CRC also sends automated text messages to help patients complete their screening tests, which extends support beyond the medical encounter. 95% of US adults own a cellphone, and there is no digital divide along racial or socioeconomic lines, which creates an opportunity to encourage healthy behaviors and potentially reduce health disparities.³⁸⁻⁴¹ Our mPATH-CRC intervention leverages the high prevalence of medical encounters and cellphone ownership to maximize its reach.

While several tests exist for CRC screening, most clinicians encourage colonoscopy, the most invasive and costly option.^{33,42} Because CRC screening rates are higher when patients can choose fecal occult blood testing, there is a critical need for interventions to help patients decide which test they prefer.^{11,43} Our mPATH-CRC program uses a validated decision aid to inform patients of the commonly used screening tests and help them select their best option,⁴⁴ a direct recommendation of the Cancer Moonshot Implementation Science Working Group Report.¹ In our previous randomized, controlled efficacy trial of 450 patients, mPATH-CRC more than doubled CRC screening rates (30% vs 15%, p=0.0001).⁴⁵ This efficacy trial demonstrated the potential for mPATH-CRC to improve screening rates,

EFFECTIVENESS AND IMPLEMENTATION OF MPATH-CRC: A MOBILE HEALTH SYSTEM FOR

COLORECTAL CANCER SCREENING

Wake Forest Baptist Comprehensive Cancer Center (WFBCCC)

WFBCCC # TBD

but the implementation was led by our research team, thereby restricting its potential for scale-up in a real-world context. This major gap is now addressed in this planned Type III hybrid implementation trial.

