4.6 Mixed-Methods Study

The mixed-methods study will examine the facilitators and barriers to maintenance (sustained use of mPATH-CRC over time). In the 12th month after each clinic’s launch date, we will identify sites who have maintained use of the mPATH program throughout the study period. To supplement the quantitative data gathered with our clinic surveys (Section 4.4.6), we will conduct semi-structured interviews with four members of each clinic: the clinic champion, one clinician, one front desk team member, and one medical assistant/nursing team member. The clinic champion will assist in the identification of the other team members for interviews based on their experience with the mPATH program. All participants will receive a \$50 gift card. Using an interview guide (Appendix C), we will explore how mPATH-CRC was incorporated in the clinic’s work flow and factors that affected maintenance such as intervention adaptations, organizational characteristics, and the champion’s role. There will be a separate version of the interview guide for clinics who have very low (or no) usage of mPATH during their participation in the study.^{56,69,70} Members of clinics that opt to discontinue use of mPATH will be interviewed as soon as practical after they discontinue use. We will interview representatives from study clinics until thematic saturation is reached. These semi-structured interviews, expected to last approximately 30 minutes, will be conducted by phone or video conference and analyzed by staff trained in qualitative methods. Interviews will be audio recorded and transcribed verbatim. Transcripts will be imported into ATLAS.ti software,⁷¹ iteratively reviewed, coded by concept, and analyzed thematically to describe the implementation and sustainability experience. Themes will be compared among clinics to determine any differences.

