6.0 Analytic Plan

6.1 Sample Size and Power

6.1.1 Primary outcome: Our primary objective is to assess differences in mPATH-CRC Reach proportion of participants who complete the mPATH-CRC program or have risk factors identified by mPATH-CheckIn) in the 6th month between the two implementation strategies. Using formulae found in Hemming et al.,⁷² **Table 3** shows the number of clinics necessary to detect differences in Reach ranging from .15 to .20 with 80% and 90% power for intraclass correlations (ICC) ranging from .03 to .08, assuming an average sample size per clinic of 30 with a cluster sample size coefficient of variation (CV) of 25%. These latter numbers are based on estimated numbers of eligible patients seen monthly, obtained from a

survey of the participating clinics. Since these data will be obtained from the EHR,

Table 3. Total number of clinics needed to detect the specified difference in Reach as a function of the power, ICC, and difference.

| Diff/ICC | 80% Power | | | | | | 90% Power | | | | | |
|----------|-----------|-----|-----|-----|-----|-----|-----------|-----|-----|-----|-----|-----|
| | .03 | .04 | .05 | .06 | .07 | .08 | .03 | .04 | .05 | .06 | .07 | .08 |
| .15 | 22 | 26 | 29 | 33 | 36 | 40 | 30 | 34 | 39 | 44 | 48 | 53 |
| .20 | 12 | 14 | 16 | 18 | 20 | 22 | 16 | 19 | 22 | 24 | 27 | 29 |

we will use all eligible patients at each site. We will recruit a total of 22 clinics, which will provide at least 80% power to detect a difference of 15% if the ICC is 0.03 or lower. If the ICC were as high as 0.08, we would have over 80% power to detect a difference of 20%. These calculations assume average utilization across all sites of 50%. Power increases as rates move away from 50% in either direction.

6.1.2 Effectiveness outcome: A secondary objective is to assess the effect of mPATH-CRC on screening rates (effectiveness) comparing 8 months of data prior to implementation to 8 months of data following implementation. The detectable difference (difference in screening rates pre vs post) depends on the sample size, power, ICC, and cluster sample size CV. We will assume a screening rate in the pre-implementation group of 15%, as observed in the control group in our R01 study.⁴⁵ Using SS/Power formulae for cluster designs^{72,73}, **Table 4** shows the differences in screening rates we will be able to detect

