6.2 Analysis of Primary Outcome

We will assess the primary hypothesis (that the “high touch” vs. “low touch” implementation strategy will result in greater use of the intervention) using a mixed effects logistic regression model with mPATH-CRC Reach (Y/N) as the individual-level outcome, implementation approach as the primary independent variable, site as a random effect, and the stratification factor clinics size as a covariate per the design. A descriptive approach will also be utilized where mPATH-CRC Reach is estimated and reported along with an exact 95% confidence interval for each month (for months 1-6 following implementation), and within socioeconomic strata for “high touch” and “low touch” clinics separately. In secondary analyses, we will assess effects of clinic-level covariates (e.g. volume, rurality, organizational culture) and patient level covariates (e.g. age, gender, race/ethnicity) on Reach. We will include arm-by-covariate interactions to determine if the effect of the implementation strategy differs depending on levels of the covariates. This secondary analysis will allow us to determine effects of the implementation strategy in clinics with varying organizational factors and populations. The proposed approach allows us to incorporate participant- and cluster-level covariates, but there are other analysis methods we could employ. For example, we could use a clinic-level analysis (e.g. analysis of covariance) on the mean implementation rates within each clinic, or another individual-level approach (e.g. generalized estimating equations). Alternative methods and their strengths and weaknesses are well-documented.⁷⁴⁻⁷⁶ These alternate approaches will be used in a sensitivity analysis to determine effects of the modeling assumptions on the results.

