 - Report that conflicts turn into fights

Analytic plan

Our primary analysis will compare the proportion of patients seen in the “pre” time period to the “post” time period who screen positive for either depression, fall risk, or safety at home. If a patient is seen more than once in a given time period, only the patient’s first visit in that time period will be included in the analyses. We will estimate the proportion who screen positive for each time period and report along with 95% confidence intervals. A chi-square test will be used to provide an unadjusted comparison between the “pre” and “post” proportions. Logistic regression models will then be used to compare the “pre” and “post” proportions while controlling for clinic and patient demographic variables. We will use the same analytic methods for our secondary outcomes. We will also conduct a sensitivity analysis for our primary outcome where we consider all patients’ visits during a given time period (and not limit analyses to a patient’s first visit in the time period only). For this sensitivity analysis, we will compare the proportion of patients who meet our primary outcome definition at any visit during the “pre” and “post” time periods.

Analytic adjustments due to COVID19 pandemic: Due to the COVID19 pandemic, all practices stopped using mPATH in March 2020, which is prior to the closure of the 60-day “post” time period for clinics #5 and #6 in our sample. Therefore, we will truncate the “post” time period for these two clinics to 30 days. To determine if this truncated time period affected our overall results, we will conduct the following sensitivity analyses: (1) limiting the analyses to only the first 4 clinics to enroll, and (2) limiting data collection to 30-days post- for all 6 clinics.

EFFECTIVENESS AND IMPLEMENTATION OF MPATH-CRC: A MOBILE HEALTH SYSTEM FOR
COLORECTAL CANCER SCREENING
Wake Forest Baptist Comprehensive Cancer Center (WFBCCC)
WFBCCC # TBD

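### Section 6.3 tests pre/post change in screening with site as the only random effect, so clinic-to-clinic variation in that change is left out of the standard error

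*Combined protocol and SAP*

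**What the plan says.** Section 6.3 compares completion of screening within 16 weeks between a pre-implementation and a post-implementation cohort from the same clinics. The model is described as similar to the Reach model of Section 6.2: "implementation cohort will be the primary independent variable, site will be a random effect", with clinic size as a covariate. The comparisons of change between strategies, and between levels of mPATH-CRC use, are made "by incorporating interactions into the mixed effects logistic regression models". No clinic-by-period term, random slope, robust variance or clinic-based degrees of freedom is written for these tests.

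Other sections bear on this:

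- Section 6.1.1 sizes Reach "for intraclass correlations (ICC) ranging from .03 to .08" and says: "These calculations assume average utilization across all sites of 50" per cent.
- Section 2.2.3 plans to classify clinics by high, low and variable maintenance, and Section 4.6 provides "a separate version of the interview guide for clinics who have very low (or no) usage of mPATH".
- Section 4.4.5 brings clinics in two at a time, matched on size, and randomises one of each pair to each strategy.
- Section 6.2 lists clinic-level and GEE alternatives for Reach: "These alternate approaches will be used in a sensitivity analysis to determine effects of the modeling assumptions on the results".
- The interrupted time series in Section 6.3 estimates clinic-specific effects through clinic interaction terms in a linear model, then compares strategies by linear contrasts.

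**The concern.** A site intercept is enough for Reach, which is measured in one period. In a two-period comparison within clinics, the shared intercept cancels from each clinic's change, and what remains in the standard error is essentially binomial. Strategy is randomised by clinic, so the natural unit for the strategy comparison is the clinic's change, and there are 22 of those. If clinics given the same strategy change by different amounts, chance differences among a few clinics can be reported as an effect of mPATH or of the strategy, with intervals that are too narrow.

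**Working it through.** **Inputs from the documents.** 22 clinics, 11 per strategy; 30 patients per clinic-month over 8 months, so m = 240 per clinic-period; cluster-size CV 25%; pre-implementation screening 15%; screening ICC .03-.06 (Section 6.1.2). Reach ICC .03-.08 at 50% use (Section 6.1.1). Screening of 15% without and 30% with mPATH-CRC in the earlier efficacy trial (Section 1.0).

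**Assumptions.** Two-sided 5% level (not stated, but it reproduces Table 4). Cluster autocorrelation (CAC): a share 1 − CAC of the between-clinic variance is specific to the period. The documents give no value for it.

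**1. Table 4 (80% power).** Detectable d solves d = (1.960 + 0.842) × √[2p̄(1 − p̄) × DE / 5280], with p̄ = .15 + d/2, 5280 = 22 × 240 and DE = 1 + (1.0625 × 480 − 1) × ICC.

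| ICC | DE | d computed | Table 4 |
|---|---|---|---|
| .03 | 16.27 | .0869 | .087 |
| .04 | 21.36 | .1009 | .100 |
| .05 | 26.45 | .1136 | .113 |
| .06 | 31.54 | .1253 | .125 |

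The table therefore behaves like a parallel comparison of 11 against 11 clusters of 480 and gives no credit for observing the same clinics twice.

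**2. What the written model assumes.** With no clinic-by-period variance, the SE of the pre/post difference is √[2 × .1275 × (1 − ICC) / 5280] = .0068 (ICC .03) and .0067 (ICC .06). If a clinic's two periods were unrelated, DE with m = 240 is 8.62 and 16.24, and the SE is √(2 × .1275 × DE / 5280) = .0204 and .0280. The written model always reports close to the smaller figure; the correct one depends on how much clinics differ in change.

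**3. Uptake variation alone, strategy test.** SD of clinic Reach = √(ICC × .25) = .087 (ICC .03) and .141 (ICC .08). If lift scales with Reach, multiplying by .30 − .15 gives an SD of clinic change of .0130 and .0212. The binomial SD of one clinic's change from 15% to 22.5% (half the full lift) is √[(.15 × .85 + .225 × .775) / 240] = .0355.

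- Variance inflation = 1 + (SD of change / .0355)² = 1.13 and 1.36.
- Type I error = 2[1 − Φ(1.96 / √inflation)] = 6.6% and 9.3%.
- On the logit scale (lift 0.887 × Reach), inflation is 1.10 and 1.28, and type I error 6.2% and 8.3%. Simulation on that scale (20,000 runs) gives 6-8%.

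If mPATH has no effect, uptake cannot make clinics' changes differ, so this source leaves the overall test at its nominal level under that null.

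**4. Other clinic-specific drift, assumed CAC.** Proportion scale: inflation = 1 + 240 × ICC × (1 − CAC) / (1 − ICC). Latent logit scale: inflation = 1 + (1 − CAC) × [ICC / (1 − ICC)] × (π²/3) × 240 × .1275. Type I error for ICC .03-.06:

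| CAC | Proportion scale | Latent scale |
|---|---|---|
| 1.0 | 5% | 5% |
| 0.95 | 9-14% | 7-9% |
| 0.9 | 14-22% | 9-13% |
| 0.8 | 21-33% | 12-20% |

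Fitting the random-intercept logistic model itself to simulated data (latent ICC .04, CAC 0.8, 1,000 runs) gave 15-18%; a clinic-level analysis of change gave 4-5%.

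**5. Pairing.** Drift common to both clinics of a pair cancels from the strategy contrast. If all of it is shared, that test stays at about 5%. If half is shared, inflation at CAC 0.8 on the proportion scale falls from 2.48 and 4.06 to 1.74 and 2.53, that is 14-22%. An unpaired 11-versus-11 t-test on clinic changes is then conservative in simulation: about 0.1-2.5% with all drift shared and roughly 2-4% with half. A paired test holds 5% throughout.

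**6. Time series level contrast between strategies.** Simulated (6,000 runs) over the same CAC range on the proportion scale: 5% to about 10%. The trend contrast stays near 5%.

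**The case against.** The strongest reply is that the large figures do not come from the plan. That stands. A reader might take 21-33% as this trial's error rate, but it needs an assumed CAC of 0.8 and a proportion-scale ICC; the latent scale gives 12-20%, and CAC 1 makes the written model valid.

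A reader might also cite the statement in Appendix D that "all practices stopped using mPATH in March 2020" as evidence against the strategy test. The documents do not support that. The remark belongs to a sub-study of six clinics, its bearing on the effectiveness cohorts is inferred, and disruption tied to launch date is largely shared within a pair. It bears mainly on the overall test.

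Nor does the gap between Table 4 and the model show that the study is underpowered or that the sponsor assumed a particular CAC. Table 4 is conservative sizing and is silent on that point.

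Partial safeguards exist. The dose interaction models much of the uptake variation directly, so it is less exposed. The time series contrast is only modestly affected, although it is not stated to use between-clinic variance. The Section 6.2 sensitivity analyses might be meant to cover effectiveness, and the site random effect might be meant to include a slope, but neither is written.

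**Conclusion.** The concern holds as a gap in the model specification for the key secondary outcome and should be fixed. The direction is certain: the pre/post and strategy-by-period tests are anti-conservative whenever true change varies between clinics in a way the model omits.

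The only size anchored in the documents is about 6-9% for the strategy test, and it rests on lift being proportional to Reach. Anything beyond that depends on a clinic-by-period variance the plan does not give and, for the strategy test, only on the part not shared within a launch pair. For the overall test the possible inflation can be shown only over an assumed range.

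**What to change.** In Section 6.3:

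- Add a random clinic-by-period effect to the overall and strategy-interaction models, with small-sample, clinic-based degrees of freedom.
- Reflect the pairing of Section 4.4.5, either by a pair-by-period term or by a paired analysis of the 11 within-pair differences in clinic-level change (10 df).
- Keep the clinic-specific time series terms for within-clinic estimates, but test the high-touch versus low-touch contrasts against between-clinic variance.
- State that the clinic-level and GEE sensitivity analyses of Section 6.2 also apply to effectiveness, with a small-sample correction for 22 clusters.
- Report the estimated clinic-by-period variance.

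This changes SAP wording only and needs no new data. Intervals widen if clinics change differently, as they should. If they do not, the cost is the smaller degrees of freedom: 2.086 / 1.96 = 1.06, about 6% wider at 20 df, and 2.228 / 1.96 = 1.14, about 14% wider at 10 df. A random-slope test is also somewhat conservative in that case (about 3% in simulation).

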2.2 Secondary Objective

2.2.2 **In a pragmatic trial, estimate the effect of mPATH-CRC on completion of CRC screening within 16 weeks of visit.** We will query the electronic health record (EHR) at each study clinic to identify individuals aged 50 – 74 with no evidence of current CRC screening at the time of their clinic visit. We will then examine in the EHR whether these individuals complete CRC screening within 16 weeks of their index visit. The primary effectiveness analysis will compare the proportion of patients who complete screening between the pre- and post-implementation period in the “high touch” vs. “low touch” clinics. A secondary analysis will explore whether there is a dose-response relationship between use of mPATH-CRC and screening rates across all clinics.

2.2.3 **Determine the factors that facilitate or impede the maintenance of mHealth interventions like mPATH-CRC.** We will assess all clinics 12 months after implementation to identify those with high, low, and variable levels of maintenance. Using mixed methods that incorporate in-depth interviews with clinic staff, providers, and administrators, we will identify theory-based and organizational factors associated with sustained use of technology-based

EFFECTIVENESS AND IMPLEMENTATION OF MPATH-CRC: A MOBILE HEALTH SYSTEM FOR

COLORECTAL CANCER SCREENING

Wake Forest Baptist Comprehensive Cancer Center (WFBCCC)

WFBCCC # TBD

interventions like mPATH-CRC. These results will provide critical information to guide future large-scale dissemination and implementation trials.

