- 5.3.10 mPATH™-CRC Maintenance: The proportion of patients aged 18 or older who complete mPATH™-CheckIn in months 7-12

EFFECTIVENESS AND IMPLEMENTATION OF MPATH-CRC: A MOBILE HEALTH SYSTEM FOR

COLORECTAL CANCER SCREENING

Wake Forest Baptist Comprehensive Cancer Center (WFBCCC)

WFBCCC # TBD

- 5.3.11 mPATH™-CRC Effectiveness: The proportion of patients aged 50-74 who are eligible for CRC screening who complete CRC screening within 16 weeks of their index visit to the clinic. Effectiveness is determined by comparing the proportion who complete screening in a pre-implementation cohort (months 12 - 4 before implementation) to a post-implementation cohort (months 1 - 8 after implementation).
- 5.3.12 CRC screening tests ordered: The outcome is defined as the proportion of patients aged 50-74 who are eligible for CRC screening who have a CRC screening test ordered (colonoscopy, flexible sigmoidoscopy, fecal testing for blood, or fecal DNA testing) within 16 weeks of their index visit to the clinic. This outcome will also be compared between the pre- and post-implementation cohorts.
- 5.3.13 Facilitators and barriers to maintenance (sustained use of mPATH™-CRC over time): These will be identified through semi-structured interviews. Interviews will explore how mPATH™-CRC was incorporated in the clinic's work flow and factors that affected maintenance such as intervention adaptations, organizational characteristics, and the champion's role. Interviews will be conducted with four members of each selected clinic: the clinic champion, one clinician, one front desk team member, and one medical assistant/nursing team member.

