Appendix B – Data Collection Instruments

The following instruments have been submitted to the IRB as pdf files:

Clinic Characteristics Survey

Clinic Staffing Form

Staff Linkage Form

Staff Consent & Contact Information Form

Staff Baseline Survey

Staff Demographics Survey

Clinic Support Log

Follow-Up Clinic Personnel Survey: 6 month timepoint

Follow-Up Clinic Personnel Survey: 12 month

Additional data collection instruments in development:

The final data collection instruments listed below have not yet been developed. Each instrument will be submitted to the IRB for formal review and approval before they are used with any human subjects. The planned data collection instruments and their descriptions are listed below.

Cost Database

All technology costs associated with implementing and maintaining mPATH will be recorded in a secure, electronic database.

mPATH-CRC Database

The mPATH-CRC database will be stored in an encrypted, HIPAA-compliant Cloud-based server with continuous data backup. The database is password protected and meets HIPAA security requirements. The database includes patient medical record numbers, date and time of use, and answers to mPATH-

EFFECTIVENESS AND IMPLEMENTATION OF MPATH-CRC: A MOBILE HEALTH SYSTEM FOR

COLORECTAL CANCER SCREENING

Wake Forest Baptist Comprehensive Cancer Center (WFBCCC)

WFBCCC # TBD

CRC survey questions (CRC screening history, CRC screening decisions, etc.). The database is password protected and access is limited to those with authorization. When the mPATH-CRC database is queried to construct our study dataset, the medical record numbers will be replaced with an anonymous study identifier by an honest broker. A full copy of the mPATH-CRC survey will be submitted to the IRB for review and approval prior to use with human subjects.

Clinic Query Database

We will query the study clinics' electronic health records and appointment systems to collect the following data elements needed for our planned analyses. Data will be collected for the time periods specified in the Experimental Methods (Section 4.0).

- Patient age
- Patient gender
- Patient race/ethnicity
- Flagged as needing a language interpreter (and language needed)
- Patient marital status
- Patient health insurance
- Patient history of colorectal cancer
- Patient history of colorectal polyps
- Patient family history of colorectal cancer
- Date of visit to clinic
- Name of provider being seen
- Name of nursing staff who roomed the patient

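### The overall pre/post effectiveness model in Section 6.3 adjusts for nothing that can change within a clinic, so a shift in patient mix goes into the period effect; a case-mix-adjusted estimate should be prespecified.

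*Combined protocol and SAP*

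**What the plan says.** Section 5.3.11 defines the outcome as a period contrast: "Effectiveness is determined by comparing the proportion who complete screening in a pre-implementation cohort (months 12 - 4 before implementation) to a post-implementation cohort". Section 6.3 gives the terms of the overall logistic model: "implementation cohort will be the primary independent variable, site will be a random effect, and the stratification factor clinic size will be a covariate". It lists no patient variable. Section 4.4.5 makes clinic size a pairing factor, fixed before each pair is randomised.

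Four other places bear on the point:

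- Section 6.3 adds, for this outcome and with reference to Section 6.2, "we will assess the effects of cluster- and patient-level covariates and their interactions with implementation strategy in secondary analyses". Section 6.2 describes that work as assessing the effects of "patient level covariates (e.g. age, gender, race/ethnicity) on Reach", together with arm-by-covariate interactions.
- Section 6.3 also plans a segmented regression by clinic, "adjusting for any trend that was occurring in screening prior to the implementation", and a comparison of the pre/post change between strategies.
- Section 2.2 describes the primary effectiveness analysis as a comparison "between the pre- and post-implementation period in the “high touch” vs. “low touch” clinics", whereas Sections 5.3.11 and 6.3 start from the overall pre/post contrast.
- Appendix D makes a similar before/after comparison in six of the trial's clinics and does adjust: "Logistic regression models will then be used to compare the “pre” and “post” proportions while controlling for clinic and patient demographic variables".

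The Clinic Query Database in Appendix B already holds age, gender, race/ethnicity, interpreter need and "Patient health insurance".

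**The concern.** Randomisation does not protect a comparison of the same clinics before and after launch. The patients in the two periods are different samples, and they may differ in characteristics that predict screening. A covariate with one value per clinic cannot correct for that, and neither can a site intercept common to both periods. Both strategies deliver mPATH, so the randomised contrast cannot show whether mPATH itself raises screening. That conclusion depends on the pre/post estimate.

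The documents give a reason not to take a stable mix for granted. Appendix D records that all practices stopped using mPATH in March 2020, before the 60-day post period of clinics 5 and 6 had closed. Unless their launch date is reset, their 8-month effectiveness window runs past that date, while their pre window ends 4 months before launch and so before it. Appendix D adapts to this and Section 6.3 does not mention it. The documents do not say whether the patient mix changed.

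**Working it through.** **Inputs from the plan (Section 6.1).** 22 clinics; 30 eligible patients per clinic per month; 8 months per period; pre-implementation rate 15%; planned difference 10 points (15% vs 25%); cluster-size CV 25%; ICC 0.03 to 0.06. Alpha for this outcome is not stated; two-sided 0.05 is assumed.

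**1. The plan's own figure.** Table 4 gives a detectable difference of 0.100 at 80% power and ICC 0.04. Design effect = 1 + ((1 + CV²)m − 1) × ICC. With m = 480: 1 + (1.0625 × 480 − 1) × 0.04 = 21.36. With 11 clinics per group, effective n = 11 × 480 / 21.36 = 247.2, and the pooled two-proportion power is 0.796. The rest of the table reproduces in the same way (power 0.796 to 0.803 and 0.898 to 0.902). Table 4 therefore matches two independent groups of 11 clinics with 480 patients each. It is not the precision of the planned model, in which the same 22 clinics are seen twice, so that precision is computed next.

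**2. Precision of the planned contrast.** Patients per period = 22 × 30 × 8 = 5,280. Between-clinic variance cancels within clinics, so SE = √(2 × 0.15 × 0.85 × (1 − 0.03) / 5,280) = 0.0068, or 0.68 points (0.69 without the ICC factor). An apparent change of 1.96 × 0.68 ≈ 1.3 points reaches p < 0.05.

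**3. Bias from a mix shift.** Bias = (change in a subgroup's share) × (gap in screening rate between subgroups). Rejection rate with no true effect = P(|Z + bias/SE| > 1.96). Shift and gap are both assumptions.

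| Shift in share | Bias, gap 5 points | Bias, gap 20 points | Rejection rate |
|---|---|---|---|
| 2 points | 0.1 | 0.4 | 5–9% |
| 5 points | 0.25 | 1.0 | 7–31% |
| 10 points | 0.5 | 2.0 | 11–83% |

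The shift at which bias equals 1.96 SE is about 27, 13, 9 and 7 points for gaps of 5, 10, 15 and 20 points. To imitate the planned 10-point effect at a 20-point gap, the shift would have to be 10/0.20 = 50 points.

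**4. Simulation.** 400 replicates, no true mPATH effect, 22 clinics with about 240 patients per period, ICC 0.04, 40% of pre-period patients in the higher-screening group, and site fixed effects standing in for the random intercept.

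| Shift, gap (points) | Period OR, unadjusted | Rejection |
|---|---|---|
| 5, 10 | 1.04 | 12% |
| 5, 15 | 1.06 | 18% |
| 10, 10 | 1.08 | 29% |
| 10, 15 | 1.13 | 62% |

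With the mix variable in the model, the OR is 0.999 to 1.005 and rejection is 4.8 to 5.5%.

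Steps 2 to 4 assume no site-by-period variation. Carrying such variation into the standard error would widen it and lower the rejection rates; the bias would not change.

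**The case against.** The strongest reply is that the plan does not rely on this model alone.

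- **Windows.** The two periods are offset by 12 months (48 weeks under Section 5.1's 4-week month), so they cover nearly the same season. This stands and removes one source of shift.
- **Segmented regression.** Gradual drift in mix would appear largely in the pre-launch trend. This also stands. However, no patient covariate is listed in that model, so a step change around launch remains.
- **High versus low touch.** A shift common to both arms largely cancels, and Section 2.2 calls this contrast primary. A reader might infer that the overall pre/post estimate is undisputedly the headline; the documents are inconsistent on that. Even so, the randomised contrast does not estimate mPATH against no mPATH, and Table 5 gives detectable interaction odds ratios of 2.9 to 4.8.
- **Secondary covariate analyses.** A reader might infer that patient covariates are ignored or ruled out for this outcome. They are not. If they were added to the overall model with cohort retained, an adjusted cohort coefficient would result. The text describes covariate effects and strategy interactions and does not commit to that estimate.
- **Appendix D as precedent.** It is imperfect: it covers six clinics, opens with an unadjusted chi-square test, and has neither a time series nor a randomised contrast. It does show that adjusting a before/after contrast for demographics is already accepted practice within this trial.

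Whether the adjusted model is the main or the supporting analysis is partly a matter of preference. That it should be prespecified with named variables is not.

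**Conclusion.** The concern holds as a gap in specification. The overall pre/post model contains nothing that controls a within-clinic change in patient mix, and no other planned analysis commits to a pre/post estimate that does.

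The size is modest to moderate and rests on assumed shifts and gaps. A reader might infer that even a small shift would pass as an mPATH effect. The numbers do not support that: shifts of 2 to 5 points bias the estimate by at most about 1 point and usually would not reach significance. Shifts of about 7 to 13 points, with gaps of 20 down to 10 points, would bring the bias to the significance threshold. A reader might also set the bias against 7.5 points, by halving the earlier efficacy trial's 15-point difference for 50% use. The plan's stated effect is 10 points, and 1.0 to 2.0 points of bias is 10 to 20% of it.

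The risk is therefore a false or distorted modest effect, in favour of mPATH or against it. Case mix could not plausibly imitate the full planned effect.

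**What to change.** In Section 6.3, include patient age, gender, race/ethnicity, insurance and interpreter need as fixed effects in the pre/post models for outcomes 5.3.11 (screening completed) and 5.3.12 (tests ordered), as Appendix D does for demographics. Report the model with cohort, site and clinic size only alongside it as a sensitivity analysis, and tabulate these characteristics by period.

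The cost is a few sentences of SAP wording and one table. All the variables are in the Appendix B query, so no new data are needed. Adjustment removes only shifts in the variables listed, so the segmented regression should stay.
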